12.3.2 Attribution Definitions

The relationship, or attribution, of an adverse event to the study therapy regimen or study procedure(s) will initially be determined by the site investigator and recorded on the appropriate AE paper case report form (AE/SAE paper CRF). Final determination of attribution for safety reporting will be determined by DAIT/NIAID. The relationship of an adverse event to study therapy regimen or procedures will be determined using the descriptors and definitions provided in Table 12.3.2.

For additional information and a printable version of the NCI-CTCAE manual, consult the NCI-CTCAE web site: <http://ctep.cancer.gov/reporting/ctc.html>.

Table 12.3.2 Attribution of Adverse Events

Code	Descriptor	Relationship (to primary investigational product and/or other concurrent mandated study therapy or study procedure)
UNRELATED CATEGORY		
1	Unrelated	The adverse event is clearly not related: there is insufficient evidence to suggest a causal relationship.

RELATED CATEGORIES

2	Possible	The adverse event has a reasonable possibility to be related; there is evidence to suggest a causal relationship.
3	Definite	The adverse event is clearly related.

12.4 Collection and Recording of Adverse Events**12.4.1 Collection Period**

Adverse events will be collected from the time of time of consent until a subject completes study participation or until 30 days after he/she prematurely withdraws (without withdrawing consent) or is withdrawn from the study.

12.4.2 Collecting Adverse Events

Adverse events (including SAEs) may be discovered through any of these methods:

- Observing the subject.
- Interviewing the subject, e.g., using a checklist, structured questioning, diary, etc.
- Receiving an unsolicited complaint from the subject.
- In addition, an abnormal value or result from a clinical or laboratory evaluation can also indicate an adverse event, as defined in Section 12.3, *Grading and Attribution of Adverse Events*.

12.4.3 Recording Adverse Events

Throughout the study, the investigator will record adverse events and serious adverse events as described previously (Section 12.2, *Definitions*) on the appropriate AE/SAE paper CRF regardless of the relationship to study therapy regimen or study procedure.

Once recorded, an AE/SAE will be followed until it resolves with or without sequelae, or until the end of study participation, or until 30 days after the subject prematurely withdraws (without withdrawing consent)/or is withdrawn from the study, whichever occurs first.

12.5 Reporting of Serious Adverse Events and Adverse Events**12.5.1 Reporting of Serious Adverse Events to DAIT/NIAID**

Site investigators will report all serious adverse events (see Section 12.2.3, *Serious Adverse Event*), regardless of relationship or expectedness within 24 hours of discovering the event.

For serious adverse events, all requested information on the AE/SAE paper CRF will be provided. However, unavailable details of the event will not delay submission of the known information. As additional details become available, the AE/SAE paper CRF will be updated and submitted.

The site investigator will report to the NIAID Medical Officer and the Independent Medical Monitor all serious adverse events within 24 hours of becoming aware of the event, regardless of relationship or expectedness.

CONTACT INFORMATION FOR NIAID MEDICAL OFFICER:

[REDACTED], MD MPH

NIAID/ DAIT/ AAABB

[name] [REDACTED]

[name] [REDACTED]

P: [REDACTED] M: [REDACTED]

Email: [REDACTED]

12.5.2 Reporting to Health Authority

[name] will be the sponsor of the IND and has the responsibility of reporting all AEs and SAEs to the FDA within the reporting time limits set forth by the FDA. It is [name] ultimate responsibility to report any serious adverse event to the Independent Medical Monitor at her site and to the NIAID Medical Monitor within 24 hours of becoming aware of the event.

After an adverse event requiring 24-hour reporting (per Section 12.5.1, *Reporting of Serious Adverse Events to Sponsor*) is submitted by the site investigator and assessed by DAIT/NIAID, there are two options for [name] to report the adverse event to the appropriate health authorities:

12.5.2.1 Annual Reporting

[name] will include in the annual study report to health authorities all adverse events classified as:

- Serious, expected, suspected adverse reactions (see Section 12.2.1.1, *Suspected Adverse Reaction*, and Section 12.2.2, *Unexpected Adverse Event*).
- Serious and not a suspected adverse reaction (see Section 12.2.2, *Suspected Adverse Reaction*).
- Pregnancies.

Note that all adverse events (not just those requiring 24-hour reporting) will be reported in the Annual IND Report.

12.5.2.2 Expedited Safety Reporting

This option, with 2 possible categories, applies if the adverse event is classified as one of the following:

Category 1: Serious and unexpected suspected adverse reaction [SUSAR] (see Section 12.2.1.1, *Suspected Adverse Reaction* and Section 12.2, *Unexpected Adverse Event* and 21 CFR 312.32l(1)i).

The sponsor shall report any suspected adverse reaction that is both serious and unexpected. The sponsor shall report an adverse event as a suspected adverse reaction only if there is evidence to suggest a causal relationship between the study drug and the adverse event, such as:

1. A single occurrence of an event that is uncommon and known to be strongly associated with drug exposure (e.g., angioedema, hepatic injury, or Stevens-Johnson Syndrome);
2. One or more occurrences of an event that is not commonly associated with drug exposure, but is otherwise uncommon in the population exposed to the drug (e.g., tendon rupture);
3. An aggregate analysis of specific events observed in a clinical trial (such as known consequences of the underlying disease or condition under investigation or other events that commonly occur in the study population independent of drug therapy) that indicates those events occur more frequently in the drug treatment group than in a concurrent or historical control group.

Certain SAEs occur commonly in this study population. Anaphylaxis to study food ingestion will be reported in the annual report, unless it is life-threatening or results in death, in which cases an expedited report will be filed.

Category 2: Any findings from studies that suggests a significant human risk

The sponsor shall report any findings from other epidemiological studies, analyses of adverse events within the current study or pooled analysis across clinical studies or animal or *in vitro* testing (e.g. mutagenicity, teratogenicity, carcinogenicity) that suggest a significant risk in humans exposed to the drug that would result in a safety-related change in the protocol, informed consent, investigator brochure or package insert or other aspects of the overall conduct of the study.

The IND Sponsor, [name], shall notify the appropriate health authorities and all participating sub investigators of safety reporting within 15 calendar days; unexpected fatal or immediately life-threatening suspected adverse reaction(s) shall be reported as soon as possible or within 7 calendar days.

12.5.3 Reporting of Adverse Events to IRBs/IECs

All investigators shall report adverse events, including expedited reports, in a timely fashion to their respective IRBs/IECs in accordance with applicable regulations and guidelines. All Safety Reports to the FDA shall be distributed by [name] or designee for site IRB/IEC submission.

12.6 Pregnancy Reporting

The investigator shall be informed immediately of any pregnancy in a study subject. A pregnant subject shall be instructed to stop taking study medication. The investigator shall counsel the subject and discuss the risks of continuing with the pregnancy and the possible effects on the fetus. Monitoring of the pregnant subject shall continue until the conclusion of the pregnancy.

The investigator shall report to the DAIT/NIAID all pregnancies within 1 business day of becoming aware of the event using the Pregnancy paper CRF. All pregnancies identified during the study shall be followed to conclusion and the outcome of each must be reported. The Pregnancy paper CRF shall be updated and submitted to the DAIT/NIAID when details about the outcome are available.

Information requested about the delivery shall include:

- Gestational age at delivery
- Birth weight, length, and head circumference
- Gender
- Appearance, pulse, grimace, activity, and respiration (APGAR) score at 1 minute, 5 minutes, and 24 hours after birth, if available
- Any abnormalities.

All pregnancy complications that result in a congenital abnormality, birth defect, miscarriage, and medically indicated abortion - an SAE shall be submitted to the DAIT/NIAID using the SAE reporting procedures described above.

12.7 Reporting of Other Safety Information

An investigator shall promptly notify the site IRB as well as the DAIT/NIAID when an “unanticipated problem involving risks to subjects or others” is identified, which is not otherwise reportable as an adverse event.

12.8 Review of Safety Information**12.8.1 Medical Monitor Review**

The DAIT/NIAID Medical Monitor shall receive annual reports from the protocol investigator compiling new and accumulating information on AEs, SAEs, and pregnancies recorded by the study site(s) on appropriate paper CRFs.

In addition, the Medical Monitor shall review and make decisions on the disposition of the SAE and pregnancy reports received by the protocol investigator (See Sections 12.5.1, *Reporting of Serious Adverse Events to Sponsor*, and 12.6, *Pregnancy Reporting*).

12.8.2 DSMB Review

12.8.2.1 Planned DSMB Reviews

The Data and Safety Monitoring Board (DSMB) shall review safety data at least yearly during planned DSMB Data Review Meetings. Data for the planned safety reviews will include, at a minimum, a listing of all reported AEs and SAEs.

The DSMB will be informed of an Expedited Safety Report in a timely manner.

12.8.2.2 *Ad hoc* DSMB Reviews

In addition to the pre-scheduled data reviews and planned safety monitoring, the DSMB may be called upon for *ad hoc* reviews. The DSMB will review any event that potentially impacts safety at the request of the protocol chair or DAIT/NIAID. In addition, the following events will trigger an *ad hoc* comprehensive DSMB Safety Review:

- Any death related to food allergen OIT dosing
- One case of severe and prolonged anaphylaxis that does not respond to 3 doses of epinephrine, or that includes intubation and that is related to food allergen dosing or to oral food challenge.
- More than 2 cases of hypotension related to food allergen dosing or to oral food challenge.
- More than 3 of either of the following events:
 - Severe adverse event, other than anaphylaxis, related to investigational product or
 - Eosinophilic esophagitis with synchronous clinical symptoms and confirmatory biopsy findings

After review of the data, the DSMB will make recommendations regarding study conduct and/or continuation.

12.8.2.2.1 Temporary Suspension of enrollment/drug dosing or both for *ad hoc* DSMB Safety Review

A temporary halt in enrollment, initial dose days and drug up dosing *will* be implemented if an *ad hoc* DSMB safety review is required per the criteria outlined in section 12.8.2.2. above.

In the event of a study halt for DSMB review, subjects in the screening phase will continue to undergo screening procedures unless the review was triggered by events related to screening. Subjects already receiving therapy will remain on study treatment at their current tolerated dose.

Based on the outcome of the DSMB review, the consent and/or assent forms may be revised. Upon approval of these revisions by the IRB, all subjects who have previously provided informed consent for the study and are affected by the new information will be re-consented.

13. Statistical Considerations and Analytical Plan

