	
non-atopic disease within 90 days preceding Initial Dose Escalation Day (IDED) or at any time after the IDED
 
 • Use of beta-blockers (oral) • Pregnancy or lactation • Allergy to oat • History of severe anaphylaxis to cashew or shrimp with symptoms including hypotension requiring fluid resuscitation and/or the need for mechanical ventilation within the last year • Use of investigational drugs within 12 weeks of participation • Past or current medical problems or findings from physical assessment or laboratory testing that are not listed above, which, in the opinion of the investigator, may pose additional risks from participation in the study, may interfere with the participant’s ability to comply with study requirements or that may impact the quality or interpretation of the data obtained from the study

Study Stopping Rules
	
During the study, if the investigator or the NIAID Medical Officer discovers conditions that indicate that the study should be discontinued, an appropriate procedure for stopping the study pending DSMB review will be instituted.
 
If any of the stopping rules listed below are met, study enrollment will be suspended, the Initial dose day will be suspended, dose escalation during Build-up will be stopped, and all enrolled participants will remain on their current dose pending expedited review of all pertinent data by the Data Safety Monitoring Board:
 
 • Any death related to cashew or shrimp OIT dosing • More than 3 cases of CoFAR Grade 4 AE related to food allergen dosing or to oral food challenge. • More than 3 participants require more than 2 injections of epinephrine during a single dosing of cashew or shrimp OIT investigational product • More than 3 of the following events: 
 ○ Severe adverse event, other than anaphylaxis, related to investigational product ○ Eosinophilic esophagitis

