
Participant Stopping Rules
	
 1. The participant elects to withdraw consent from all future study activities, including follow-up. 2. The participant is “lost to follow-up” (i.e., no further follow-up is possible because attempts to reestablish contact with the participant have failed). 3. The participant dies. 4. The Investigator no longer believes participation is in the best interest of the participant. 5. Individual safety stopping rules: 
 a. Anaphylaxis resulting in hypotension, neurological compromise or mechanical ventilation secondary to OIT dosing or food challenge

	
 b. Any subject deemed to have severe allergic reactions and who receives aggressive therapy (e.g., hypotension with IV fluid resuscitation, mechanical ventilation, more than 2 doses of epinephrine for a life-threatening reaction) at any time should be discontinued from further therapy c. Other circumstances including, but not limited to, the following: 
 ○ Severe adverse event, other than anaphylaxis, related to investigational product ○ Pregnancy

Premature Discontinuation of Investigational Agent
	
 • Poor control or persistent activation of secondary atopic disease (e.g., AD, asthma), at the discretion of the investigator • Started on beta-blockers, or other prohibited medications, with no alternative medications available per the prescribing physician • Non-adherence with home OIT dosing protocol (excessive missed days more than 20 days) without consulting with study staff would be a safety issue warranting discontinuation • The subject develops biopsy-documented eosinophilic esophagitis (EoE) with synchronous clinical symptoms or other eosinophilic gastrointestinal disease 
Study therapy may also be prematurely discontinued for any participant if the investigator believes that the study treatment is no longer in the best interest of the participant.

Table of Contents

Study Definitions Page	14
1. Background and Rationale	16
1.1. Background and Scientific Rationale.....	16
1.2. Rationale for Selection of Investigational Product or Intervention.....	16
1.3. Preclinical Experience	16
1.4. Clinical Studies	17
2. Study Hypotheses/Objectives.....	17
2.1. Primary Objective(s).....	18
2.2. Secondary Objective(s)	18
2.3. Exploratory Clinical objectives:	18
2.4. Safety Objectives.....	18

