5.3. Risks of Study Procedures

Food allergen dosing (Initial dose day; Updosing; Oral food challenges):

A potential serious risk associated with the administration of food allergen is the risk of anaphylaxis. Symptoms of anaphylaxis may include pruritus, urticaria, angioedema, wheezing, cough, dyspnea, emesis, diarrhea, and hypotension that may progress to hypotensive shock.

The potential discomforts with the Initial dose day procedure, up dosing procedure, and oral food challenges are similar to the exposure to the suspected food in the past. Symptoms are usually transient lasting less than 2 hours and include pruritus, urticaria, nausea, abdominal discomfort, emesis and/or diarrhea, rhinitis, and sneezing and/or wheezing. The major risks involved include respiratory distress and rarely anaphylactic shock. Medication, personnel, and equipment are immediately available in the SNPRU to treat allergic reactions. Subjects will be provided a prescription and training for an EpiPen® or EpiPen, Jr.® or equivalent to have with them at all times and to use in case of an allergic reaction.

Phlebotomy:

Risks associated with phlebotomy or insertion of an intravenous catheter include infection, syncope, and localized pain, stinging, bleeding, or contusions at the phlebotomy site where the needle is inserted into the vein.

Skin prick test:

The risk involved with skin testing includes discomfort from the needle prick, along with erythema, urticaria, pruritus, and swelling at the skin test site in positive responses. Rare side effects include severe allergic reactions.

Spirometry:

The risk of a lung function test is the discomfort of exhaling forcefully. This may be associated with mild shortness of breath, slight dizziness, temporary cough and/or chest discomfort. Most patients do not have any symptoms.

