300mg, 600mg, 1000mg and 2000mg. . Both food allergens (cashew or shrimp) and oat protein will be concealed in a food that masks the taste. After the last dose of the DBPCFC, the subject will be monitored for 2 hours and then discharged home. Subjects will be considered to have tolerated the OFC if they do not experience any objective reactions by Appendix aa.

If the subject experiences reactions, they will be treated with the necessary rescue medications. They will be observed for a minimum two hours after the final administered dose and discharged home only when deemed clinically stable by a study physician.

After the Week 52 DBPCFC, subjects who meet the following criteria will discontinue FA protein daily dosing entirely:

- On OIT treatment for 52 weeks,
- Taking daily maintenance dose of 1000 mg protein for approximately 3 weeks,
- No severe reactions (CoFAR criteria) to home dosing, and/or

Subjects who do not pass a cumulative of 2043 mg at Week 52 will be considered desensitization failures. They will be considered in statistical analyses of the intent-to-treat population. They will be followed until the end of study (week 58).

After Week 52, all subjects will begin their withdrawal phase for 6 weeks.

On Study DBPCFC (Week 58, Week 64): At Week 58 subjects will have a DBPCFC to up to 4043 mg to assess sustained unresponsiveness (tolerance). The visit will also include a physical assessment, spirometry, fecal matter collection, skin prick test, and blood draw for mechanistic studies.

During the oral food challenge, there should be increased hydration (i.e. about 16 oz or more given orally). There are no published data indicating whether repeating food challenges every 6 weeks will or will not maintain desensitization or otherwise affect the outcomes in this study. Our preliminary studies in which we have performed DBPCFCs every 3 months in a separate phase 1 study cohort (n=87 subjects) have demonstrated no increased risk of sensitization (as per repeat cumulative doses on repeat DBPCFC and as per severity of reaction).

End of study (Week 58 or Week 64): Participants will be followed until week 58 or until Week 64 if they opt to continue avoidance of OIT for 8 more weeks after Week 58.

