11.5. Study Stopping Rules

During the course of this study, if the investigator or the NIAID Medical Officer discovers conditions that indicate that the study should be discontinued, an appropriate procedure for stopping the study pending DSMB review will be instituted, including notification of the FDA and IRB. See section 12.8.2.2

12. Safety Monitoring and Reporting

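### The death trigger in both study-halt lists names only OIT dosing, so a food-challenge death does not automatically bring an ad hoc DSMB review and pause

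*Combined protocol and SAP*

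**What the plan says.** Two lists govern a halt. The synopsis (Study Stopping Rules) suspends enrollment, initial dose days and dose escalation when any of its lines is met. Section 12.8.2.2 lists events that trigger an ad hoc comprehensive DSMB review, and Section 12.8.2.2.1 attaches a temporary halt to that review.

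The death lines are "Any death related to cashew or shrimp OIT dosing" in the synopsis and "Any death related to food allergen OIT dosing" in 12.8.2.2. Other lines go further. The synopsis has "More than 3 cases of CoFAR Grade 4 AE related to food allergen dosing or to oral food challenge", and in 12.8.2.2 the anaphylaxis and hypotension lines likewise cover both dosing and oral food challenge.

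Elsewhere, the synopsis rule for stopping an individual participant refers to "mechanical ventilation secondary to OIT dosing or food challenge", and Section 12.2.1 states that challenge material does not count as study drug and that challenge reactions are recorded separately. Section 11.5 adds a general clause: if the investigator or the NIAID Medical Officer finds conditions indicating that the study should be discontinued, "an appropriate procedure for stopping the study pending DSMB review will be instituted".

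**The concern.** Food challenges are a main source of acute risk in this trial. They take place at screening, at weeks 52 and 58, and optionally at week 64. The authors named challenges where they meant to include them, yet the line for the worst outcome leaves them out.

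Read literally, this reverses the order of seriousness. A participant who survives a severe, prolonged challenge reaction with intubation triggers a mandatory review and halt. A participant who dies quickly in a challenge, without intubation and before three epinephrine doses have failed, does not. At stake is whether enrollment and dosing stop automatically while the DSMB looks at the event, in a trial that enrolls children from age 7.

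**Working it through.** No formula applies, and the plan states no figure to reproduce. The check takes one death caused by a food challenge, assumes no earlier qualifying events, and tests it against every line of both lists.

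**Synopsis, Study Stopping Rules**

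| Line | Met by one challenge death? |
|---|---|
| Death related to OIT dosing | No: challenge not named |
| More than 3 CoFAR Grade 4 events, dosing or challenge | No: one case, and death is Grade 5 (Section 12.3.1) |
| More than 3 participants needing more than 2 epinephrine injections at a single OIT dosing | No: one participant, and OIT dosing only |
| More than 3 severe non-anaphylaxis events related to product, or eosinophilic esophagitis | No: one event, and challenge material is not study drug (Section 12.2.1) |

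Result: 0 of 4.

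**Section 12.8.2.2**

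| Line | Met by one challenge death? |
|---|---|
| Death related to OIT dosing | No: challenge not named |
| One case of severe, prolonged anaphylaxis, dosing or challenge | Only if three epinephrine doses failed or intubation took place |
| More than 2 hypotension cases, dosing or challenge | No: one case |
| More than 3 severe non-anaphylaxis events related to product, or confirmed eosinophilic esophagitis | No: one event |

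Result: 0 of 4 unconditionally, 1 of 4 if the anaphylaxis conditions hold.

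**Could OIT dosing be read to include challenges?** One heading points that way: Section 5.3 has "Food allergen dosing (Initial dose day; Updosing; Oral food challenges", which places challenges under food allergen dosing. Three things count against it. The death lines say OIT dosing, not food allergen dosing. The Grade 4, anaphylaxis and hypotension lines list challenge in addition to food allergen dosing, which would be redundant if dosing already included it. The participant stopping rule sets OIT dosing and food challenge side by side as alternatives.

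**Screening is the clearest case.** The screening challenge (Section 8.2) precedes the Initial Dose Day, so a death there cannot be related to OIT dosing on any reading. Yet Section 12.8.2.2.1 provides for reviews triggered by screening events, so the list was meant to reach that phase.

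**What else would apply to such a death**

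- Section 12.5.1: SAE report to the NIAID Medical Officer and the Independent Medical Monitor within 24 hours.
- Section 12.8.1: the Medical Monitor reviews SAE reports and decides on their disposition.
- Section 12.5.2.2: an expedited report for anaphylaxis to study food that is life-threatening or fatal, in wording not restricted to OIT doses.
- Section 12.8.2.1: timely notice of expedited reports to the DSMB, and DSMB safety review at least yearly.
- Section 12.8.2.2: DSMB review at the request of the protocol chair or DAIT/NIAID.
- Synopsis and Section 11.5: the general stopping clause.

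Each of these brings the death to someone's attention. None makes the ad hoc review and the pause follow without a further decision.

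**The case against.** The strongest reply is that the gap hardly matters in practice. Fatal anaphylaxis in a challenge must be reported by the expedited route and the DSMB told promptly. The general clause leaves judgement only over whether conditions warrant stopping; once they are recognised, a stopping procedure follows. It is hard to imagine a challenge death not being recognised. Challenges are physician-supervised, with a crash cart and a code team available, so a fatal arrest would plausibly involve intubation or repeated epinephrine and meet the anaphylaxis line. If two hypotension cases had already occurred, a hypotensive challenge death would also meet the hypotension line. All of this stands. It makes the gap narrow, but does not make the review and pause automatic.

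Two stronger readings are tempting and are not supported.

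A reader might infer that a challenge death could go unreviewed. The reporting and review duties above make that remote.

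A reader might also infer that the halt text lets on-study challenges carry on, so that a mandatory pause at weeks 52, 58 and 64 is needed. The text is silent on those challenges, and "After Week 52, all subjects will begin their withdrawal phase for 6 weeks" means that an instruction to stay on the current dose fits poorly after week 52. But the synopsis says "all enrolled participants will remain on their current dose pending expedited review of all pertinent data by the Data Safety Monitoring Board". If that phrase arguably holds back a week 52 challenge, it arguably holds back the later ones too, since those participants are enrolled and their current dose is nil. Nor would a count of all week 58 and week 64 challenges measure the exposure, because a halt is temporary and affects only challenges that fall inside it. A pause would also move the timing of the week 52 challenge, on which the primary comparison rests, and of the week 58 challenge that defines sustained unresponsiveness. That trade-off is better weighed by the DSMB when the event occurs.

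**Conclusion.** The point holds as a narrow drafting gap in a safety rule. As a first qualifying event, one challenge death meets 0 of 4 synopsis triggers. In 12.8.2.2 it meets 1 of 4 if the anaphylaxis conditions hold, and otherwise none. The uncovered cases are mainly a rapid anaphylactic death without intubation or three failed doses, and a non-anaphylactic death related to a challenge.

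This rests on reading OIT dosing as excluding challenges, which the neighbouring lines support, and on the challenge being done under this protocol; screening challenges may also be done under a separate screening protocol. The event is very unlikely, and the documents give no rate for it. The figure below 0.1% in Section 5.2 (risks cited in the medical literature) concerns life-threatening anaphylactic reactions and has no stated unit. The change is worth making because it costs almost nothing, not because the present text leaves participants unprotected.

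**What to change.** Use one wording for the death line in both the synopsis stopping rules and Section 12.8.2.2: "Any death related to food allergen OIT dosing", followed by *or to oral food challenge*.

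The cost is a few words in two places, carried in a protocol amendment with the IRB approval that Section 16.1 requires. It needs no new data or staff and changes no endpoint or analysis. If such a death occurred, enrollment, initial dose days and updosing would stop until the DSMB had reviewed it, which is the purpose of the list. No mandatory pause of the week 52, 58 or 64 challenges is proposed; the DSMB can decide that at its review.
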